8.4 Randomization

This study will investigate 2 treatment groups:

Group (Treatment)	Treatment Assignment
1 (A/B)	DST-0509 / Jadenu (Exjade)
2 (B/A)	Jadenu (Exjade) / DST-0509

A computer-generated randomization scheme will be used to obtain a balanced allocation to each treatment group.

8.5 Statistical Analyses

A comprehensive statistical analysis plan (SAP) will be written and approved prior to database lock for this study that describes the final analyses to be completed for safety, efficacy, and pharmacokinetic endpoints.

Data collected in this study will be presented using summary tables, figures, and patient data listings. Summary tables will present data by treatment group and by time of collection. Continuous variables will be summarized using descriptive statistics, specifically the number of patients (n), the mean, median, standard deviation, minimum and maximum, and coefficient of variations (%CV). Categorical variables will be summarized by frequencies and percentages. Confidence intervals will be provided where appropriate for derived endpoints. Figures will be used to support the presentation of certain data. Sensitivity analyses may be performed to examine the effect of missing data.

All confidence intervals (CIs), statistical tests, and resulting p values will be reported as 2-sided. Significance will be assessed at $\alpha = 0.05$ level and the significance level will not be adjusted for multiple comparisons in the exploratory efficacy endpoint analyses.

8.5.1 Demographics and Baseline Characteristics

Demographic data (age, gender, race, body weight, height, and BMI) will be recorded.

8.5.2 Efficacy Analyses

Planned efficacy analyses will include examination of changes in iron chelation. Analysis by TDT and NTD stratification will depend on recruitment status. Descriptive summaries of serum ferritin at each time point in each study period will be completed. Change from baseline in

serum ferritin will be assessed with a mixed model for repeated measures (MMRM) to assess changes within each treatment period and time. Categorical summaries will be presented for efficacy responders, i.e., the proportion of patients who achieve serum ferritin <800 mcg/L.

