8. Other criteria, at the Investigator's discretion in consultation with the Medical Monitor.

DOSAGE FORMS AND ROUTE OF ADMINISTRATION:

DST-0509 will be supplied in 360 mg, 180 mg and 90 mg tablets. Jadenu is commercially available as tablets and Exjade as tablets for oral suspension and will be provided by the patient with their ongoing prescription. Dosing will be at equivalent (mg for mg) doses of DST-0509 or Jadenu. If converting from Exjade, the dose will be scaled for each treatment by 28 mg/40 mg (treatment/Exjade).

This is an open-label crossover study. Patients will receive Exjade or Jadenu at their previous stable dose. DST-0509 is taken with food, Jadenu is taken with or without a light meal, and Exjade is recommended to be taken without food. However, either Jadenu or Exjade can be administered according to the patient's previous regimen.

OUTCOME VARIABLES:

The primary outcome of the study will be the safety, overall tolerability, and preliminary evidence of DST-0509 iron chelating activity compared to Jadenu or Exjade.

Iron chelation

Serum ferritin will be assessed at screening (Visits 1 and 2) and on Days 1, 28, 36 and 63. Change from baseline in each treatment period will be assessed as the main efficacy variable for serum ferritin.

Efficacy responders, i.e., the proportion of patients who achieve serum ferritin <800 mcg/L, will be evaluated.

Pharmacokinetics

Trough deferasirox levels will be collected in the Screening period at approximately -4 and -2 weeks. Blood samples for PK analysis will be collected predose (-0.5 hour for trough level) and at 1, 2, 4, and 8 hours post dose on Days 1, 7, 28, 36, 42 and 63. The PK parameters of DST-0509 and Jadenu or Exjade will be derived from the concentration time data. The allowed sampling "window" is ± 15 min for the 1 and 2 hour time points, and ± 30 min for the 4 hour time point. For the 8 hour time point, the allowable window is ± 1 hour.

The goal of the PK analyses will be to characterize the PK of the inadequate responder population on their current DFX therapy at the end of 4 weeks compared to 4 weeks of therapy with DST-0509. The hypothesis is that a significant proportion of inadequate responders will have low exposures on current therapy compared to exposure with DST-0509.

Exploratory Pharmacogenomics

A blood sample will be taken at Visit 2 to collect germline DNA to allow for later exploratory sub-analyses of genotype vs exposures.

SAFETY AND TOLERABILITY ASSESSMENTS:

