2 OBJECTIVES

2.1 Primary

This patient-pilot study will assess the safety, overall tolerability, and preliminary evidence of DST-0509 iron chelating activity compared to Jadenu or Exjade in patients with transfusion-dependent beta thalassemia (TDT), major or intermedia, or non-TDT patients with inadequate response to available deferasirox chelation therapy, defined as a liver iron (Fe) concentration (LIC) of at least 5 mg Fe/g dw and a serum ferritin greater than 800 mcg/L.

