7.10 Ferritin Monitoring

Ferritin (mcg/L) will be assessed in serum or plasma (at Screening, Eligibility and on Days 1, 28, 36 and 63) with enzyme-linked immunosorbent assays (ELISA) by routine laboratory methods.

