8.5.4.2 Statistical Analysis

Statistical analyses will be generated using SAS (version 9.0 or higher) for the Mixed procedure. The natural logarithmic transformation of PK parameters as well as the rank-transformation of T_{max} will be used for all statistical inference. Subjects who do not have parameters for both DST-0509/Jadenu or DST-0509/Exjade treatments will not be included in the respective statistical bioequivalent analyses.

Exposure pharmacokinetic parameters (C_{max} , AUC) will be statistically analyzed using an Analysis of Variance (ANOVA) model. The fixed factors included in this model will be the treatment received, the period at which it was given as well as the sequence in which each treatment is received. A random factor will also be added for the patient effect (nested within sequence).

The 90% confidence interval for the exponential of the difference in LS means between Treatments will be computed. If there are sufficient data for both Jadenu and Exjade, both will serve as reference in the respective analysis, no pooling of data between the reference treatments (Jadenu, Exjade) will be performed.

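### The stated aim of the ferritin MMRM, change within each period, does not match the protocol's objective of comparing DST-0509 with Jadenu/Exjade

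*Protocol*

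**What the plan says.** - **Objective (section 2.1; also in the synopsis).** Among the primary aims is "preliminary evidence of DST-0509 iron chelating activity compared to Jadenu or Exjade in patients" with inadequate response. Section 3.2 gives comparison of safety, tolerability and efficacy as the reason for the crossover.
- **Variable (synopsis, Outcome Variables).** "Change from baseline in each treatment period will be assessed as the main efficacy variable for serum ferritin".
- **Model (section 8.5.2; same wording in the synopsis).** The ferritin change goes into an MMRM whose only stated purpose is "to assess changes within each treatment period and time". No fixed effects, random effects or contrast are listed. The other ferritin analyses are descriptive summaries and a categorical summary of responders.
- **Timing (section 7.10).** Ferritin is measured "at Screening, Eligibility and on Days 1, 28, 36 and 63".
- **PK, for contrast (section 8.5.4.2).** "The fixed factors included in this model will be the treatment received, the period at which it was given as well as the sequence" of treatments, with patient nested in sequence as random and a 90% CI for the LS-mean difference between treatments. The two reference products are not pooled there.
- **Status of the SAP (sections 8 and 8.5).** Full details are left to a SAP. The protocol says it summarises the key aspects.

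**The concern.** The objective is a difference between treatments. The declared purpose of the one model that could deliver it is change inside a period. A SAP written to that purpose would comply with the protocol and still leave the objective unanswered.

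A before/after change in one period is not a treatment effect. Patients enter because ferritin exceeded 800 mcg/L on two screening assessments (section 4.1), so some regression to the mean is to be expected. Each period's baseline follows seven days off chelation (section 7.6), and transfusion support is allowed. Influences common to both treatments cancel in the crossover contrast but stay in a within-period change.

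Section 8.5 sets a two-sided 0.05 level and makes no multiplicity adjustment for exploratory efficacy. If only within-period results are reported, readers are likely to set the p-value on DST-0509 beside the p-value on the comparator. That is not a test of their difference, and it gives up the within-patient comparison for which the crossover was chosen.

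**Working it through.** **Plan's own figure.** The protocol gives no effect size, SD or power for ferritin. Section 8.1 excludes chelating activity from the sample size. Its only figures concern diarrhea: at a 12% rate and N=30, P(at least 1) = 1 − 0.88^30 = 0.978 and P(at least 2) = 0.890. These match the stated 98% and 89%, and they do not bear on this point.

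**Step 1: what is repeated.** Period 1 has Day 1 (baseline) and Day 28. Period 2 has Day 36 (baseline) and Day 63. Change from baseline therefore gives one value per period and two per patient. There is no repeated time inside a period. The repetition is across periods, and that is where the treatment contrast lies.

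**Step 2: what each contrast estimates.** Let A and B be the mean changes on DST-0509 and the comparator, and let π be the period effect. Allocation is 1:1.
- Calendar period 1 mean: (A + B)/2.
- Calendar period 2 mean: (A + B)/2 + π.
- Period 2 minus period 1: π. The treatment difference cancels.
- Crossover contrast, half the between-sequence difference in (period 1 − period 2): ½[(A − B − π) − (B − A − π)] = A − B.

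A simulation (4,000 runs, N=36, true A − B = −0.5 SD, π = 0, within-patient correlation 0.5) gave a mean calendar-period contrast of −0.002 SD. The crossover contrast averaged −0.501 SD and was significant in 83% of runs.

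**Step 3: reading two separate tests side by side (assumed inputs).** Take N=30, one of the sizes tabulated in section 8.1, and a true change d that is the same on both treatments, so the true difference is zero. The range of d and the within-patient correlation ρ are assumptions.
- Power of each one-sample t-test (29 df, noncentrality d√30, two-sided 0.05) is p.
- With independent periods, P(exactly one significant) = 2p(1 − p).
- With ρ = 0.5, the same probability comes from simulation.

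| d (SD) | d√30 | p | Disagree, ρ = 0 | Disagree, ρ = 0.5 |
|---|---|---|---|---|
| 0.3 | 1.64 | 0.355 | 2 × 0.355 × 0.645 = 0.46 | 0.31 |
| 0.4 | 2.19 | 0.563 | 2 × 0.563 × 0.437 = 0.49 | 0.34 |
| 0.5 | 2.74 | 0.754 | 2 × 0.754 × 0.246 = 0.37 | 0.26 |

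A separate simulation at N=36 and d = 0.33 SD gave disagreement in 33% (ρ = 0.5) to 51% (ρ = 0) of runs. The crossover contrast rejected in about 5%, its nominal level.

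**The case against.** The best defence is that section 8.5.2 names a model class and a loosely worded purpose. It lists no terms and excludes none, and an MMRM with treatment, period and sequence would fit the sentence. Model terms are commonly left to the SAP, which is not shown here. Fuller detail for PK does not make the shorter efficacy text wrong.

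Most of this stands. A reader might infer that the protocol fixes a within-period analysis and that no treatment difference will be estimated. The text does not support that. It also plans one mixed model, not two separate tests, and nowhere says that two p-values will be compared. Step 3 therefore illustrates a risk of misreading; it is not a property of the written plan. A reader might also take the upper part of that range as this trial's risk, but it needs independent periods, which is implausible for the same patients crossed over, and an effect size with no source in the protocol.

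The deferral to the SAP does not remove the point. The protocol undertakes to give the key aspects, and for ferritin it does state a purpose. That purpose differs from its own objective.

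The trial is a pilot, chelating activity is labelled preliminary, efficacy is called exploratory, and no decision rule hangs on a ferritin test. That limits the weight.

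**Conclusion.** The point holds as a mismatch between stated aim and objective. The protocol asks for a comparison of chelating activity, its only ferritin model is described as serving within-period change, and no section names the treatment contrast. With one post-baseline value per period, following that aim literally yields before/after changes only.

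The weight is moderate. The data to be collected do support the right estimate, and the wording leaves room for it. The 26% to 49% disagreement range is illustrative and depends on N=30, equal true changes of 0.3 to 0.5 SD, and correlation between 0.5 and 0. The mismatch itself depends on none of these assumptions.

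**What to change.** In section 8.5.2 and the matching synopsis paragraph, state that:
- the ferritin model estimates the DST-0509 minus comparator difference in period-specific change, with treatment, period and sequence as fixed effects and patient within sequence as random;
- the main ferritin result is the LS-mean difference with a 95% CI;
- Jadenu and Exjade are, or are not, pooled as the comparator for ferritin. Section 8.5.4.2 bars pooling for PK, and borrowing its model terms leaves this open. Without pooling, the up to 36 patients split by product in a mix that the protocol does not fix;
- within-period changes are descriptive.

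A log scale and the period baseline (Day 1, Day 36) as covariate are optional and can be left to the SAP. The cost is one short paragraph in two places, with no new visits, samples or patients.

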8.5.3 Safety Analyses

Adverse Events

Adverse experiences will be coded using Medical Dictionary for Regulatory Activities (MedDRA, version 20.0 or higher) and summarized by System Organ Class (SOC) and Preferred Term for each treatment group. All AEs will be captured after the first dose through the final visit (Visit 11) or the ET visit.

Adverse events will be summarized by presenting:

- the number and percentage of patients experiencing any AE
- the number and percentage of patients experiencing any AE grouped by SOC
- the number and percentage of patients experiencing any SAE
- the number and percentage of patients experiencing any AE associated with study discontinuation.

Gastrointestinal Adverse Events of Special Interest (GI AESI)

In addition, safety will also include assessing adverse events of special interest (AESI) including selected gastrointestinal AEs of diarrhea, constipation, nausea, vomiting, and abdominal pain.

Other Safety and Tolerability Parameters

At each clinic visit, treatment exposure will be estimated with compliance rates based on patient diary cards and pill counts, and tolerability will be assessed by general enquiry and specific iron chelation tolerability questions as well as by patient diaries concerning tolerability. Study patients will receive a diary to record gastrointestinal (GI) adverse events (AEs) of special interest (AESI) during the course of the study. Patients will be given the Bristol Stool Chart with diary and instructed on its use to help them characterize the nature of the bowel movements. All AE's will be monitored throughout the trial.

Patient safety will be monitored per clinical standard of care including routine laboratory monitoring. This will include monthly CBC, chemistry panel, and urinalysis assessments. Urine will be collected to measure protein: creatinine ratio and serum CRP will be assessed.

Compliance

Patients will be responsible for supplying their own Jadenu or Exjade during the study. Pill counts will be performed at each visit in order to characterize patient compliance (calculated as % doses taken per protocol). Additional measures of compliance will include Investigator enquiry into patient prescription refill records if available, satisfaction with iron chelation therapy (SICT) questionnaire [ref 8; [Appendix D](#)] and use of patient diaries.

Dose reductions

Dose reductions/interruptions of DST-0509 and Jadenu/Exjade are discouraged. However, in the event of a severe or higher AE lasting for >7 days, the PI, at their discretion, may reduce the dose by 25-33% or interrupt dosing. Max interruption is seven days. Dose re-escalation is not permitted. When AE resolves or is mild, the patient may restart study from last dose visit per PI or Medical Monitor (MM) discretion.

Dose suspension

Dosing with either treatment should be suspended in event of significant cytopenia – platelet count <50,000/ml or ANC <1,500/ml. If cytopenia has not recovered to Grade 1 or less after suspension of treatment for 7 days, the patient will be withdrawn from the study. The rationale for inclusion or exclusion of these subjects in the PK Population will be documented and listed.

Clinical Laboratory Parameters

Clinical laboratory measurements (serum chemistry, hematology and urinalysis) and changes from baseline will be summarized descriptively for each visit with the mean, median, standard deviation (SD), minimum and maximum, by treatment group.

Additionally, shifts from low, normal or high at baseline to low, normal or high at the end-of-treatment will be tabulated and presented by treatment group.

Vital Signs

Vital signs will be summarized descriptively for the mean, median, SD, minimum, and maximum by treatment group.

ECOG Performance Status

The ECOG performance status will be assessed at Screening Visit 1, and on Days 1, 28, 36 and 63. (see [Appendix C](#)). Changes from baseline will be presented with categorical descriptive statistics.

ECG Evaluation

ECG will be evaluated on Day 1 (Visit 3) and must be acquired predose and before blood samples are collected, and after a 5 min rest in supine position to avoid artifacts. Results will be provided in a patient listing.

Bristol Stool Chart Assessment

The Bristol Stool Chart (Section 7.13) will be used to evaluate average stool consistency: “What was the average stool consistency for the last 24 hours?” Stool Consistency will be presented with categorical description (N, % of patients) by visit for each consistency parameter: hard, lumpy, sausage, snake, soft, mushy or liquid. No formal inferential analysis will be conducted.

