Exposure and safety parameters

At each clinic visit, treatment exposure will be estimated with compliance rates based on patient diary cards and pill counts, and tolerability will be assessed by general enquiry and specific iron chelation tolerability questions as well as by patient diaries concerning tolerability. Study patients will receive a diary to record gastrointestinal (GI) adverse events (AEs) of special interest (AESI) during the course of the study. Patients will be given the Bristol Stool Chart with diary and instructed on its use. All AE's will be monitored throughout the trial after the first dose.

Patient safety will be monitored per clinical standard of care including routine laboratory monitoring. This will include monthly CBC, chemistry panel, and urinalysis assessments. Urine will be collected to measure protein: creatinine ratio and serum CRP will be assessed.

Compliance

Patients will be responsible for supplying their own Jadenu or Exjade during the study. Pill counts will be performed at each visit in order to characterize patient compliance (calculated as % doses taken per protocol).

Additional measures of compliance will include Investigator enquiry into patient prescription refill records if available, satisfaction with iron chelation therapy (SICT) questionnaire [ref 8; [Appendix D](#)] and use of patient diaries.

Dose reductions

Dose reductions/interruptions of DST-0509 and Jadenu/Exjade are discouraged. However, in the event of a severe or higher AE lasting for 7 or more days, the PI, at their discretion, may reduce the dose by 25-33% or interrupt dosing. The maximum interruption allowable is seven days. Dose re-escalation is not permitted. When AE resolves or is mild, the patient may restart study from last dose visit per PI or Medical Monitor (MM) discretion.

Dose suspension

Dosing with either treatment should be suspended in event of significant cytopenia (platelet count <50,000/ml or ANC <1,500/ml). If cytopenia has not recovered to Grade 1 or less after suspension of treatment for 7 days, the patient will be withdrawn from the study.

STATISTICAL ANALYSES:

A comprehensive statistical analysis plan (SAP) will be written and approved prior to database lock for this study that describes the final analyses to be completed for safety, efficacy, and pharmacokinetic endpoints.

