4.3 Patient Withdrawal Criteria

Patients may be removed from the study for reasons including the following:

1. Significant protocol violation on the part of the Investigator or patient;
2. Significant noncompliance on the part of the patient as determined by the Investigator in consultation with the Medical Monitor;
3. Patient withdraws consent;
4. During the study, patient has the need for medications, supplements, ingredients and herbal therapies that are excluded (see [Section 7.4](#), "Prohibited Medications" for examples in each category; this list is not all inclusive);
5. Unacceptable toxicity based on laboratory or other clinical findings, based on PI opinion;

6. Occurrence of any adverse event (AE) or condition that could, in the Investigator's opinion, interfere with the evaluation of the treatment effect or put the patient at undue risk;
7. Pregnancy; or
8. Other criteria, at the Investigator's discretion in consultation with the Medical Monitor.

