6.6 Early Termination Procedures

The term "Early Termination" refers to a patient's non-completion of a study whether by his or her own choice or the Investigator's decision or due to discontinuation of the study by DisperSol.

In the absence of a medical contraindication or significant protocol violation, every effort will be made by the Investigator to keep the patient in the study. Should the patient decide to

withdraw, an attempt will be made to conduct an early termination visit, which will include all procedures normally done at Visit 10 (Day 63) and, the patient should be requested to undergo a 7-day washout and have a phone call to confirm as in the Follow-up (Day 70) procedures.

The primary reason for a patient withdrawing prematurely should be selected from the following categories:

Adverse Event or Serious Adverse Event - events that are associated with discontinuation.

Noncompliance with protocol - The patient failed to adhere to the protocol requirements. The deviation necessitated premature termination from the study.

Pregnancy - The patient became pregnant after enrolling the study. Pregnant patients are withdrawn from the study as soon as the Principal Investigator is aware of the condition.

Laboratory Abnormality - Laboratory abnormality that does not meet the definition of an AE.

Withdrawal of Consent - The patient desires to withdraw from further participation in the study in the absence of an adverse event or a medical need to withdraw.

Lost to Follow-up - The patient did not return for follow-up visit(s) following dispensing of test drug.

Other - causes of premature termination from the study other than the above, such as theft or loss of investigational product, termination of study by DisperSol, etc.

The Investigator should notify Accelovance, Inc. promptly when a patient is withdrawn, or if the study is stopped at his/her site by the IRB or if the Investigator elects to stop the study.

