9 ADVERSE EVENT MONITORING

9.1 Definition

An AE is defined as any untoward medical occurrence in a patient or clinical investigation following the patient's first dose of investigational product that does not necessarily have a causal relationship with this treatment. An AE can be any unfavorable or unintended sign (including an abnormal finding), symptom, or disease temporally associated with the use of a medicinal (investigational) product, whether or not related to the medicinal (investigational) product.

This includes any occurrence that is new in onset or aggravated in severity or frequency from the baseline condition (including the physical examination), or abnormal results of diagnostic procedures (including laboratory test abnormalities).

Events should be considered AEs if they:

- result in discontinuation from the study,
- require treatment or any other therapeutic intervention,
- require further diagnostic evaluation (excluding a repetition of the same procedure to confirm the abnormality),
- are associated with clinical signs or symptoms judged by the Investigator to have a significant clinical impact.

Clinically Significant Laboratory Changes: It is the Investigator's responsibility to review the results of all laboratory tests as they become available. For each abnormal result, the Investigator needs to ascertain whether the abnormality presents a clinically significant change from baseline. If the change is due to the expected course of the patient's underlying disease (e.g., elevated cholesterol in a study of dyslipidemia), it is not considered an adverse event unless the abnormality is more severe than expected. A laboratory test may be confirmed by repeat testing or other diagnostic tests before being considered an adverse event. If the laboratory abnormality is a significant change from baseline for the patient, then it should be considered an adverse event.

An Adverse Event is not:

- A surgical procedure
- A situation where an untoward event did not occur, (e.g. a social hospitalization)
- The disease being studied, unless progression is more severe than anticipated
- Lack of efficacy
- Baseline conditions that have not worsened in severity or frequency
- Clinically significant abnormal laboratory findings or test results related to the disease being studied (unless more severe than expected)

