9.3 Severity

Adverse events are first graded according to seriousness and then severity. The seriousness of an event is determined by the regulatory criteria in Section 9.6.

The Investigator will evaluate the severity of each AE. Adverse events will be graded as

Mild: Awareness of symptoms but easily tolerated

Moderate: Discomfort enough to interfere with but not prevent daily activity

Severe: Unable to perform usual activity

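### The one stated dose-reduction trigger rests on functional severity and about 7 days' duration, so a symptom-free creatinine rise would ordinarily not meet it, although both appended labels direct a step-down for a confirmed rise of 33% or more

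*Protocol*

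**What the plan says.** Section 8.5.3 (Dose reductions) discourages reductions and interruptions of DST-0509 and the comparator alike. It then gives a single condition: "in the event of a severe or higher AE lasting for >7 days, the PI, at their discretion, may reduce the dose by 25-33" percent, or interrupt for at most seven days, with no re-escalation. The Synopsis has the same rule with a different duration: "in the event of a severe or higher AE lasting for 7 or more days".

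Section 9.1 brings laboratory changes into the adverse-event definition: "If the laboratory abnormality is a significant change from baseline for the patient, then it should be considered an adverse event". Section 9.3 grades severity by its effect on the patient's activity, and the top level reads "Severe: Unable to perform usual activity".

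The one laboratory value tied to a dosing action on treatment is the blood count. The Dose suspension paragraph of Section 8.5.3 gives platelet and neutrophil limits and a withdrawal rule, "If cytopenia has not recovered to Grade 1 or less after suspension of treatment for 7 days". Creatinine appears as a screening exclusion above 1.5 times ULN (Section 4.2) and as part of the metabolic panel (Section 7.11.1), but has no on-treatment limit.

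Three other provisions bear on the point. Section 8.5.3 states "Patient safety will be monitored per clinical standard of care including routine laboratory monitoring". Section 4.3 allows removal for "Unacceptable toxicity based on laboratory or other clinical findings, based on PI opinion". Section 6.6 lists as a reason for early termination a "Laboratory abnormality that does not meet the definition of an AE".

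Section 2.5 of both appended labels covers adults with transfusional overload. After a creatinine rise of 33% or more, the test is repeated inside a week. If the rise persists, the dose is cut by 10 mg/kg (Exjade, Appendix A) or 7 mg/kg (Jadenu, Appendix B). Therapy stops above 2 times ULN or below 40 mL/min creatinine clearance.

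**The concern.** Creatinine elevation is a well-described toxicity of this drug, is usually found by blood test, and is called dose related in Section 6.1 of both labels. A trigger that needs functional incapacity for about a week does not suit it. An investigator who follows the written rule is told that reductions are discouraged and is given a condition that a silent rise ordinarily does not satisfy. The labels of the two comparator drugs say to act.

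The setting adds weight. Patients enter at the maximal dose (Section 4.1). DST-0509 is given mg for mg with Jadenu (Section 5.1), although it was more bioavailable in single-dose healthy-volunteer studies (Section 1.2). Safety is a primary objective (Section 2.1). Without a common threshold, the same creatinine result may be handled differently between sites or, in an open-label trial, between treatments.

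**Working it through.** **1. Does a silent rise meet the trigger?** A significant rise can be recorded as an adverse event (9.1). Severe means that usual activity is impossible (9.3), and a symptom-free patient does not fit that. The remaining route is seriousness: Section 9.3 has events graded by seriousness before severity, and Section 9.8 counts important medical events as serious. The trigger's extension above severe could therefore cover a serious event. So the rise would ordinarily not meet the trigger, but could if judged serious.

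**2. Is the size of the reduction at fault?** Entry doses are 28 mg/kg (Jadenu) and 40 mg/kg (Exjade).
- Jadenu label step: 7/28 = 25%.
- Exjade label step: 10/40 = 25%.

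Both lie inside the protocol's 25-33%, so for transfusional overload only the trigger needs changing. For NTDT the label step is 50%, defined at 10 or 20 mg/kg (Exjade) and 7 or 14 mg/kg (Jadenu). The label NTDT maxima are 20 and 14 mg/kg (Appendix B, 2.3). The entry doses of 40 and 28 mg/kg are twice these, so no label NTDT step applies directly.

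**3. Margin to the labels' stopping limit.** Entry allows creatinine up to 1.5 times ULN. A 33% rise from that limit gives 1.5 × 1.33 = 1.995 times ULN, practically at the stop of 2 times ULN. This describes only a patient at the limit; no distribution is given.

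**4. When could a reduction act?** Chemistry is drawn on Days 1, 14, 28, 36, 49 and 63 (7.11.3).
- Day 14: 28 − 14 = 14 doses remain in the period, or 28 − 21 = 7 if the repeat takes a full week.
- Day 49: 63 − 49 = 14, or 63 − 56 = 7.
- The ±1-day visit windows move these counts; a Day 13 draw leaves 28 − 13 = 15.
- Day 28: washout follows, but a repeat within a week falls before Period 2 starts on Day 36 and so can bear on the Period 2 dose.
- Day 63: trial dosing has ended.

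No confirmatory draw is scheduled. The next chemistry after Day 14 or Day 49 is 14 days later.

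**5. How many patients?** No 28-day rate is given. In label Study 1, 113/296 = 38.2% had rises above 33% on two occasions and 25/296 = 8.4% required reductions. Assuming a constant hazard over 48 weeks, the proportion in w weeks is 1 − (1 − p)^(w/48). For 36 patients:

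| Starting figure | 4 weeks | 8 weeks |
|---|---|---|
| 8.4% (needed reduction) | 0.7%, 0.3 patients | 1.5%, 0.5 patients |
| 38% (rise on two occasions) | 3.9%, 1.4 patients | 7.7%, 2.8 patients |

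This is illustration only. Study 1 patients were starting assigned doses; trial patients have had more than 3 months of stable maximal dosing.

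**6. PK cost of a reduction.** The half-life is 8-16 h (1.1), so 7 days is 168/16 = 10.5 to 168/8 = 21 half-lives, and end-of-period exposure would reflect the reduced dose. With exposure proportional to dose and a 25% cut in one treatment only, k reduced patients among n change the unadjusted geometric mean ratio by a factor of 0.75^(k/n), taking the cut on DST-0509.
- 1 of 36: 0.75^(1/36) = 0.992, a shift of 0.8%.
- 3 of 36: 0.75^(3/36) = 0.976, a shift of 2.4%.
- 1 of 18 in a reference-specific analysis: 0.75^(1/18) = 0.984, a shift of 1.6%.

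A cut on the comparator shifts the ratio by about the same amount in the other direction.

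**The case against.** The protocol is not silent on laboratory safety. Section 9.1 makes the investigator review every laboratory result as it arrives, judge each abnormal one for clinically significant change, and allows repeat testing. Section 9.5 lists dose reduction and interruption among the actions recorded for any adverse event, whatever its severity. The Dose reductions paragraph advises against changes and uses permissive language. Both labels are appended in full, and investigators may well apply them to the patient's own prescribed drug. Periods are short and chemistry is drawn about every 14 days on treatment.

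All of this stands, and it rules out two stronger readings. A reader might infer that the protocol forbids a step-down for creatinine, or that such a rise can never meet the trigger. The permissive wording and Section 9.5 do not support the first, and the seriousness route in Section 9.3 does not support the second. A reader might also take the 38% from Study 1 as the share of trial patients affected; the different starting point and duration do not support that.

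These provisions still do not supply the missing rule. None gives a number at which to repeat or reduce. The standard-of-care sentence concerns monitoring, and nothing invokes the labels' dose-modification sections. Withdrawal removes a patient whom a step-down might keep, in a trial that does not replace drop-outs (Section 4).

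There is also a fair objection to copying the label rule unchanged. Its baseline is taken before therapy begins, whereas Day 1 here follows a 7-day washout after months of treatment. If creatinine falls during washout (an assumption), resuming the usual dose could cross 33% without new toxicity.

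**Conclusion.** The point holds as a gap in a clinical dosing rule and should be fixed. The written trigger, followed literally, steers investigators away from a step that both appended labels direct in adults with transfusional overload, for a dose-related toxicity in patients at maximal dose. It is not something a statistical analysis plan would supply.

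The size is modest. Existing safeguards give partial protection. The expected number affected is unknown and probably small, and a reduction started within a period acts on about 7 to 14 of 28 doses, give or take the visit windows. The missing threshold is clear from the text. That a silent rise falls outside the trigger depends on its not being judged serious. The PK figures assume dose-proportional exposure and a 25% cut in one treatment only.

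**What to change.** Amend the Synopsis and Section 8.5.3 for DST-0509 and the comparator alike, regardless of functional severity or event duration:

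- **Confirm:** if creatinine is 33% or more above a stated pre-dose baseline, repeat it within 1 week.
- **Reduce:** if confirmed, cut by 7 mg/kg (DST-0509, Jadenu) or 10 mg/kg (Exjade), to the nearest whole tablet.
- **Stop:** discontinue for creatinine above 2 times ULN or creatinine clearance below 40 mL/min.
- **Baseline:** use one baseline for both periods. A post-washout Day 1 value is not the label's pre-therapy baseline, so the clinical team should confirm the choice.
- **NTDT:** the clinical team sets the step, because the entry doses exceed the label's NTDT maxima.
- **Between periods:** a Day 28 rise confirmed during washout also informs the Period 2 dose.
- **Duration:** use one 7-day wording for the existing adverse-event trigger in both places.

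The cost is a short text amendment, occasional unscheduled creatinine draws, and the small shift in the end-of-period PK comparison shown above.
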